**Virtual Reality in Labor and Delivery for Reduction in Pain**

**NCT03437031**

**Unique Protocol ID: Pro00050082**

**June 25, 2021**

## **Title: Virtual Reality for pain reduction in Labor and Delivery**

**Principal Investigators: [name], [name], [name], [name], MPH and [name], MPH**

### Purpose and Hypothesis

The purpose of this study is to identify whether use of virtual reality devices can improve the pain management of women in labor and delivery. We hypothesize that use of virtual reality devices will result in a reduction in pain medication use, in epidural use, and prolong the duration of time prior to the patient receiving an epidural.

### Background

The use of both medical and non-medical pain management in labor and delivery is ubiquitous in the United States. Among patients who undergo a vaginal delivery, 61 percent will require the use of epidural or spinal analgesia during their intrapartum course, with the highest rate of use being among Caucasian patients and those with higher levels of education (Osterman, 2011). However, many women choose complementary and alternative approaches to pain management in labor. These have included approaches as varied as hypnosis (termed hypnobirthing), biofeedback, acupuncture, and aromatherapy, with varying degrees of effectiveness (Tournaire, 2007).

As virtual reality technology has become more accessible in recent years, its utility in healthcare has been studied in several venues, mostly in its ability to reduce pain through a principle known as distraction analgesia. Virtual reality has been shown to be effective in reducing pain among patients requiring burn care (Das, 2005), during physical therapy (Hoffman, 2000), and even in the context of added noxious stimuli. Beyond even the subjective assessments of pain, the use of virtual reality has been shown to have an effect on the functional MRI findings in these patients, showing reductions in the degree of activity increases in areas usually associated with noxious stimuli.

A feasibility study of Virtual Reality has already been performed at our institution, and their findings indicated that younger patients were more open to attempting the use of the virtual reality system. Most users reported a positive experience with the system. There were no significant adverse outcomes, apart from some describing the goggles as uncomfortable (Mosadeghi, 2016). In addition, a prospective comparative cohort study was likewise performed at our institution which demonstrated a reduction in pain in the virtual reality-exposed cohort as compared to those subjects who were exposed to a calming nature video on a high-definition laptop (Tashjian, 2017).

We aim to perform a similar study to the latter above, but focused on relieving contraction pain in labor and delivery. We hypothesize that the use of virtual reality will reduce the patient's pain to a greater degree than no intervention. We will also qualitatively examine the subjects' satisfaction with and experience of virtual reality in labor and delivery as well as whether it had any effect on their need for pain medications or choice to receive an epidural.

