#### Post-Intervention Procedures

At the completion of either the VR or the Control intervention, the patients will be asked to Quantitative Patient Survey again, this time asking whether the preceding intervention would affect their responses to the questions.

A physician or authorized study staff member will collect blood pressure and pulse rate using standard sphygmomanometers in hospital wards, self-reported pain vitals, and assess coping. Then, the study staff member will ask the patient a series of questions about their experience (See Post-Intervention surveys in Additional Information).

Patients will spend 40 minutes to 1 hour with a member of the study staff during the inpatient stay, including both the initial intervention and interview time. Responses to the qualitative interview will not be audio- or video-recorded; instead, responses will be transcribed and later coded using qualitative data analysis software by study staff. Vitals collected immediately before and after the intervention will be recorded electronically; pain ratings up to 96 hours before and after intervention will be retrieved from the EHR by authorized study staff for analysis. All survey responses will be entered into a secure Redcap on a protected CSHS server.

Between participants, the VR device will be cleaned as detailed below.

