## 8. Responses to **Qualitative Interview**

### Sample Size Calculations

We will compile data from qualitative interviews, and summarize key points about the intervention brought up by patients. This report will further guide development and refinement of the inpatient VR intervention.

We will also examine changes in scores on patient-reported pain, blood pressure and pulse rate. We will compute change scores for each of these measures and also compare these patients to the Control group. If data are normally distributed, we will use a paired Student's t test for comparisons pre- and post-intervention, and two-sample t tests for between group comparisons. If data are abnormally skewed, we will conduct similar analyses using the non-parametric Wilcoxon signed-rank test, and the Wilcoxon rank-sum test, respectively.

We are uncertain of the degree of change we will observe in patient responses to the Quantitative Patient Survey (PROMIS + CSEI), pain ratings, and cardiac vitals after exposure to the VR intervention, as a study of this type has not been previously conducted.

We have decided instead to use established, clinically-meaningful changes in pain ratings as a means of estimating change. Previous studies have shown that for the minimum clinically important difference in pain scores varies by baseline starting pain level. For those subjects starting with a baseline pain level of 40-70 mm (as in our planned cohort), the minimum clinically important difference is 13 mm (Olsen, BMC Medicine 2017).

For all analyses, we will assume a 5% Type I error rate (alpha) and a 20% type II error rate (or 80% power). If we assume that the baseline median pain level of our patients is 55 mm, then for within group analyses to show a 13 mm reduction in pain would require 20 patients in each arm for 40 patients total.

Therefore, to conduct one RCT of the effect of VR on pain starting at a median level of 55 mm, we would need 40 patients:

[Control (20 patients)]

[VR (20 patients)]

We will also perform between group analyses, we will compare pain scores obtained from all inpatients exposed to the VR intervention to the Control. Our calculated sample size will also be adequate to identify a difference between groups.

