### Birth Preferences for Pain

What are your plans for coping with labor pain? (circle all that apply)

Acupuncture, acupressure, aromatherapy, biofeedback, hypnosis, massage therapy, hydrotherapy (tub), oral pain medications, IV pain medications, epidural, other

Did you attend childbirth education classes? (Yes/No)

Have you taken classes/training in any of the following methods of coping with labor pain?

Acupuncture, acupressure, aromatherapy, biofeedback, hypnosis, massage therapy, hydrotherapy (tub)

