**Perceived Effects of Participation:**

Do you think that wearing the device affected your anxiety level? [IF YES:] How so?

Do you think that wearing the device affected your pain? [IF YES:] How so?

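### The qualitative aim on pain medication and epidural choice has no matching question in the interview script or the post-session survey

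*Combined protocol and SAP*

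**What the plan says.** The aims paragraph of the Background reads "We will also qualitatively examine the subjects' satisfaction with and experience of virtual reality in labor and delivery", and the same sentence continues "as well as whether it had any effect on their need for pain medications or choice to receive an epidural". One verb and one adverb govern both halves.

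The qualitative analysis is described under Sample Size Calculations: "We will compile data from qualitative interviews, and summarize key points about the intervention brought up by patients". Neither medication nor the epidural is named there.

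Post-Intervention Procedures sets the timing. After the post-session vital signs, pain score and coping assessment, "Then, the study staff member will ask the patient a series of questions about their experience". It adds: "Patients will spend 40 minutes to 1 hour with a member of the study staff during the inpatient stay", a period described as "including both the initial intervention and interview time". No later interview is described.

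The closest scripted question, under Perceived Effects of Participation, is "Do you think that wearing the device affected your pain? [IF YES:] How so". Medication and the epidural do appear in a patient questionnaire before the session, among the answers to "What are your plans for coping with labor pain? (circle all that apply". That item has no counterpart afterwards.

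Outcomes and Data Collection lists, as secondary outcomes, IV medication need and epidural request during the intervention (3 and 4) and time to each afterwards (3a and 4a). Data item 6 records first use of each.

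**The concern.** The Background commits the study to a qualitative finding that the instruments do not ask for. If the script is followed as printed, remarks about medication or the epidural arise only by chance. Silence from a participant would then be uninterpretable: it could mean that VR had no effect on her decision, or that nobody asked.

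The subject is not peripheral. The opening hypotheses concern medication use, epidural use and time to epidural. A report on how women saw VR bearing on those decisions would be a natural companion to the recorded event times, and the plan as written does not systematically provide it.

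**Working it through.** The plan gives no figure to reproduce here. The check sets the aim against each instrument and then places the interview in time.

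**Interview script (Post-Intervention Qualitative Survey), questions by section**

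| Section | Questions | Naming medication or epidural |
|---|---|---|
| Think-aloud probe | 1 | 0 |
| Participating in the intervention | 2 | 0 |
| The VR device | 5 | 0 |
| VR experiences | 8 | 0 |
| Perceived effects | 2 | 0 |
| Future directions | 2 | 0 |
| Closing open question | 1 | 0 |
| Total | 1 + 2 + 5 + 8 + 2 + 2 + 1 = 21 | 0 |

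The two perceived-effects questions cover anxiety and pain.

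**Post-session survey.** The modified Childbirth Self-Efficacy Inventory has 15 coping behaviours. None names medication or an epidural.

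**Pre-session survey.** The birth-preferences section lists oral and IV medication and the epidural among planned methods. It is not repeated, so a change of intention over the session cannot be seen.

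**Timing**

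- Inputs: a session of up to 30 minutes (Subject Participation End), an interview of 10 to 15 minutes (interview introduction), and staff contact of 40 to 60 minutes in total (Post-Intervention Procedures).
- Session plus interview: 30 + 10 = 40 to 30 + 15 = 45 minutes, which fits the stated contact.
- Latest start of an interview that finishes within the contact: 60 − 15 = 45 to 60 − 10 = 50 minutes after staff arrive.
- Prior pain medication and epidural use are exclusions (Study Population and Period), so first use falls during or after the session.
- A need or request during the session (outcomes 3 and 4) comes before the interview. Use after the session (3a and 4a) can fall at any later time, and nobody returns to ask about it.

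So even the women who have already made a choice by the time of the interview are not asked about it. The rest could be asked only about intention, and are not asked that either.

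**The case against.** The strongest reply is that the question is already answered, and better, by the randomised comparison. Outcomes 3 to 4a and data item 6 record analgesia in both arms, and a comparison with a no-intervention control is sounder evidence of effect than the attributions of some 20 unblinded VR users. The Background sentence speaks of whether there was an effect and does not mention the woman's belief about it, so the fault may be one loosely placed adverb. Much of this stands. It makes rewording the sentence a legitimate alternative and keeps the point minor. It does not remove the mismatch, because as written the sentence puts this aim under qualitative examination. The analyses under Sample Size Calculations name pain, blood pressure and pulse, and specify none for medication or epidural use.

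A second reply is that the script is open-ended. The think-aloud probe, the question on feelings, the follow-up on pain and the closing question could all bring the topic up. That is true, so it would be wrong to say that the interviews can speak only to anxiety, pain and the device. Chance mentions still do not give systematic coverage.

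**Conclusion.** The point holds as a minor mismatch between a stated qualitative aim and its instruments: 0 of 21 interview questions and 0 of 15 post-session survey items address it, and there is a single interview directly after the session. It assumes that the printed script is the whole script and that the Background sentence means what its grammar says.

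Three stronger readings are tempting, and the documents do not support them.

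- *That no data are collected on this aim.* Analgesia use is recorded in both arms. What is missing is systematic qualitative data.
- *That the interview comes before these choices are made.* This is not true of needs and requests during the session. The documents give no figure for how many choices fall later, so only a general statement about the later ones is safe.
- *That about 12 of the 20 VR women would choose an epidural later and never be asked.* This comes from applying the Background's 61% to the arm (0.61 × 20 = 12.2). That figure is for epidural or spinal analgesia in vaginal deliveries generally, not for nulliparous women with pain of 4 to 7 and no earlier analgesia. It also treats every epidural as chosen after the interview, and it leaves out medication and the decision to decline. It does not measure the gap.

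The quantitative hypotheses do not depend on the interview.

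**What to change.** Add one question under Perceived Effects of Participation, asked at the existing post-session interview: *Did using the device change whether or when you asked for, or plan to ask for, pain medication or an epidural? How?* The wording covers women who have already asked and those who have not. The cost is about a minute of interview time, and part of what is collected will be intention.

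Optionally, repeat the birth-preferences item on planned coping methods after the session in both arms, alongside the survey that is already repeated, so that a change in intention can be described by arm. This adds one item and no patients.

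If the sponsor does not want the question, reword the Background sentence so that qualitative examination covers satisfaction and experience only, and this aim rests on the between-arm comparison of outcomes 3 to 4a. The analysis text should then name that comparison. This costs only drafting.

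An interview after delivery is not proposed. It would be a new staff contact beyond those the protocol describes, and the mismatch can be resolved without it.

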### **Study Procedures**

This protocol is a randomized controlled trial of patients in labor at Cedars-Sinai Hospital.

### Study Population and Period

The study population will consist of 40 patients: 20 in the VR arm and 20 in the Control arm (see below for sample size calculations).

We anticipate the recruitment and intervention portion of the study to be completed within 12 months.

The Inclusion criteria are as follows:

1. Female
2. >18 years old
3. English-speaking
4. Able to understand the goals of the study and provide informed consent
5. Pregnant with term gestation
6. Nullipara
7. Pain due to contractions rated from 4-7
8. Contractions at least every 5 minutes x 30 minutes preceding

The Exclusion criteria are as follows:

1. Parous
2. Use of medications for pain relief prior to the intervention
3. Use of an epidural
4. Preterm gestation
5. Pain not due to contractions
6. Pain score of 3 or below or 8 or above
7. Preeclampsia with severe features, eclampsia
8. History of epilepsy, dementia, or other neurologic disease that would prevent using VR
9. Sensitivity to flashing light / motion
10. Medical condition predisposing to nausea or dizziness
11. Injury to the eyes, face, neck, or arms that prevents comfortable use of VR hardware or software, or safe use of the hardware (e.g., open sores, wounds, or skin rash on face)

### Patient Recruitment

Patients will be recruited by three methods. First, their obstetricians will be made aware of the study, given a study flyer, and asked to inform their patients of the ability to try alternative digital pain management options during their labor course. Second, patients will be informed of the availability of the study during their prenatal classes which are offered by the obstetric nurses at Cedars-Sinai. They will be encouraged to contact study staff ([name]) on admission if they are interested in participating. Last, flyers will be present in labor and delivery making patients aware of the study and asking them to inform their nurse who will then inform study personnel ([name]) if they are interested in participating.

### Pre-Intervention Procedures

The study staff member will arrive at bedside, explain the risks and benefits of the study, and will obtain informed consent. Next, a physician or authorized study staff member will collect blood pressure and pulse data using standard sphygmomanometers in hospital wards, and will ask the patient to report current pain level on a 0 to 10 scale. We will also assess coping (Roberts, 2010) by asking "How are you coping with your labor?" We will also obtain all pain ratings collected and documented in the EHR during the current hospitalization up to 96 hours

before the intervention. Additionally, the study staff member will administer the **Quantitative Patient Survey** -- included at the end of this document and based on the NIH PROMIS Global Health Survey (10 items) and Childbirth Self-Efficacy inventory (15 items).

When a patient expresses interest in the study, she will then undergo randomization to either the VR arm or the Control arm of the study. Group assignments will be maintained inside sequentially numbered, sealed, opaque envelopes. After informed consent, study personnel will then open the assigned envelope and the study treatment will be revealed. Patients, providers, and study personnel will not be blinded to the assigned intervention.

For those patients randomized to VR, the study staff member will explain the use of the Samsung VR goggle set, and thereafter will allow the patient to use the device freely for up to 30 minutes. Intervals of 2-5 minutes is suggested for first-time use, and patients will be to allowed to discontinue it at any time as long as they are not experiencing any discomfort or side effects (dizziness, motion sickness, etc.). The study staff member will be present at all times, and will work with hospital staff as necessary to ensure the patient is receiving appropriate clinical care throughout the duration of the intervention.

For those patients randomized to the Control, the study staff member will explain that their assignment has been to the standard of care for which is no specific dedicated intervention at this time. Rather their intervention will only be further assessment of their pain scores, vitals, and medication use.

#### Post-Intervention Procedures

At the completion of either the VR or the Control intervention, the patients will be asked to Quantitative Patient Survey again, this time asking whether the preceding intervention would affect their responses to the questions.

A physician or authorized study staff member will collect blood pressure and pulse rate using standard sphygmomanometers in hospital wards, self-reported pain vitals, and assess coping. Then, the study staff member will ask the patient a series of questions about their experience (See Post-Intervention surveys in Additional Information).

Patients will spend 40 minutes to 1 hour with a member of the study staff during the inpatient stay, including both the initial intervention and interview time. Responses to the qualitative interview will not be audio- or video-recorded; instead, responses will be transcribed and later coded using qualitative data analysis software by study staff. Vitals collected immediately before and after the intervention will be recorded electronically; pain ratings up to 96 hours before and after intervention will be retrieved from the EHR by authorized study staff for analysis. All survey responses will be entered into a secure Redcap on a protected CSHS server.

Between participants, the VR device will be cleaned as detailed below.

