#### Subject Participation End

The subject's participation will be completed when they wish to discontinue either intervention or at 30 minutes.

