### VR Software

Next, we will continue to work with AppliedVR to develop appropriate VR environments for use by laboring patients. We will refine these environments given feedback from CSMC staff. These environments are not being developed specifically for any particular patient, and any participant may select any module. These modules will use 3D visual and audio cues to immerse the patient. Software modules may be used for as long as a patient wishes, but for this study, we are recommending 2-5 minutes for first use, and a maximum of 20 minutes for total use time per session.

Proposed VR interventions include the following:

1. Paint Studio: The patient will move his or her head around to paint an abstract image on canvas. Paint strokes are controlled by movement speed. Patients can also tour their own art studio.
2. TheBluVR: Patients select from several ocean environments (e.g., Arctic) by touching a trackpad on the side of the Gear VR goggles. Sea creatures swim up to the patient.
3. Concert Performance: Watch Cirque du Soleil perform from the stage. The patient can look around the environment in 360 degrees as the performance happens.
4. World Flyover: Patients fly over photorealistic views of world landmarks, allowing them to visit famous places from the hospital bed.

5. Pain RelieVR: Patients shoot at targets in an energetic cartoon world, while soothing music plays.

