### **Outcomes and Data Collection**

Primary Outcome: Reduction in pain scores from pre- to post-intervention

Secondary Outcome:

1. Duration of use of the intervention
2. Acceptability of the intervention
3. Need for IV pain medication during the intervention
  - a. Time to IV pain medication after the intervention
4. Request for an epidural during the intervention
  - a. Time to epidural use after the intervention
5. Vital sign changes during and after the intervention including heart rate and blood pressure.

Data Collection

1. Baseline maternal demographics
  - a. Name and Medical Record Number (secured and stored separate from all other data below)
  - b. Age
  - c. Race/Ethnicity
  - d. Insurance status
  - e. Gravidity/Parity
2. Admitting diagnosis
3. Obstetric data
  - a. Gestational age
  - b. Induction agents
  - c. Mode of delivery
4. Vital Signs (blood pressure, heart rate) before, during (continuous pulse oximeter and blood pressure measurements every 10 minutes) and after the intervention.
5. Pain scores before and after the intervention. Average Pain Rating during 4 hours before intervention, and Average Pain Rating after intervention (up to 24 hours).
6. Pain interventions including time to first use of IV pain medication and first use of epidural.
7. Responses to **Quantitative Patient Survey** (PROMIS Global Health pre-intervention, and modified Childbirth Self-Efficacy Inventory pre- and post-intervention)

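### The primary post-intervention pain score has no common assessment time, so its timing can differ by arm and depend on response to VR

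*Combined protocol and SAP*

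**What the plan says.** The combined protocol and SAP defines the primary outcome (Outcomes and Data Collection) as the reduction in pain score from pre- to post-intervention, without naming a minute. Post-Intervention Procedures starts the post-intervention step "At the completion of either the VR or the Control intervention". It lists the repeat survey first, then blood pressure, pulse, pain and coping. Subject Participation End says that "participation will be completed when they wish to discontinue either intervention or at 30 minutes".

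The two arms reach that point differently:

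- **VR.** Under Pre-Intervention Procedures, staff "will allow the patient to use the device freely for up to 30 minutes", and the patient may stop sooner. VR Software recommends "a maximum of 20 minutes for total use time per session". The Risks section adds a 15-minute pause for patients with symptoms, and does not say whether the pause counts toward the 30 minutes or triggers the post score.
- **Control.** Under Pre-Intervention Procedures, "their intervention will only be further assessment of their pain scores, vitals, and medication use".

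"Duration of use of the intervention" is a secondary outcome, so the plan expects stopping times to vary. For the analysis, the Sample Size Calculations section says "We will compute change scores for each of these measures and also compare these patients to the Control group". It uses two-sample t or rank-sum tests with no term for elapsed time. The time of the pain score is not among the listed data items.

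**The concern.** The Background hypothesises that VR will reduce "pain to a greater degree than no intervention", so the between-arm contrast carries the claim. That contrast is clean only if both arms are scored at comparable times. Two mechanisms can break this.

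1. **Drift.** If pain changes over the session and the arms are scored at different elapsed times, part of the difference is the course of labor and not VR.
2. **Response-dependent timing.** A woman who removes the headset because it is not helping is scored at a moment selected by her own response. Control has no matching event.

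Randomisation does not protect against either, because the assessment time is determined after allocation. The trial is also unblinded, so patient and staff know the arm when the session ends. Without recorded times, the effect could not even be examined afterwards.

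**Working it through.** **The passages side by side.** The post score follows completion, and completion is the patient's wish or 30 minutes. For VR the wish relates to a device. For Control there is nothing to take off, so the only fixed end is 30 minutes, although the wording also lets a Control patient end early. The one fixed schedule within the session is blood pressure every 10 minutes; it does not include pain. Nothing in the plan makes the two arms' times coincide.

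**Inputs from the documents.** 20 per arm, a 13 mm difference, alpha 5%, power 80%, and VR limits of 20 and 30 minutes. I take tests as two-sided; the plan does not say.

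**The plan's own figure.** No SD is given, so 20 per arm cannot be reproduced directly. It can be inverted. For a paired t test with n = 20, the noncentrality is 13 × √20 / SD, and 80% power requires SD = 19.7 mm. I use that value, with 14.3 mm and 25 mm as the range. At 14.3 mm the two-sample test has 80% power for 13 mm.

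**Assumptions not in the documents.** Pain rises 1 to 4 mm per 10 minutes, VR has no effect, Control is scored at 30 minutes, and all VR patients are scored at the same minute.

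**Drift.**

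Bias = slope × (Control time − VR time) / 10

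Noncentrality = bias / (SD × √(2/20)), with 38 degrees of freedom. At SD 19.7 mm the denominator is 6.22 mm.

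| Slope (mm per 10 min) | VR at 20 min: bias | Type I error | VR at 10 min: bias | Type I error |
|---|---|---|---|---|
| 1 | 1 mm | 5.3% | 2 mm | 6.1% |
| 2 | 2 mm | 6.1% | 4 mm | 9.6% |
| 3 | 3 mm | 7.6% | 6 mm | 15.6% |
| 4 | 4 mm | 9.6% | 8 mm | 24.0% |

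As a share of 13 mm, the bias is 8% to 31% for the 20-minute stop (1/13 to 4/13) and 15% to 62% for the 10-minute stop (2/13 to 8/13). A simulation of 200,000 trials at 1, 2, 4 and 8 mm gave 5.2%, 6.1%, 9.7% and 24.0%.

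| SD | VR at 20 min: type I error | VR at 10 min: type I error |
|---|---|---|
| 14.3 mm | 5.5% to 13.9% | 7.2% to 40.7% |
| 25 mm | 5.2% to 7.8% | 5.7% to 16.7% |

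**Reversed timing.** If Control ends at 10 minutes and VR at 20, the bias is 1 to 4 mm against VR. At SD 19.7 mm, power for a true 13 mm between-arm difference is 53.0% with no bias. It falls to 46.8%, 40.6% and 29.1% at 1, 2 and 4 mm.

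**Response-dependent stopping (stylised).** Assume no VR effect, no drift and six readings 5 minutes apart, with independent noise about baseline. Each VR patient is scored at her first reading more than 10 mm above baseline, otherwise at 30 minutes; Control is scored at 30 minutes. VR then looks worse by 1.3, 8.8 and 14.5 mm for noise SDs of 5, 10 and 15 mm. Check at 10 mm: P(reading > 10) = 0.159, so P(any of six) = 1 − 0.841⁶ = 0.645. The mean is 0.645 × 15.25 − 0.355 × 2.88 = 8.8 mm. Independent noise and an exact trigger are strong assumptions, so this shows that the mechanism can act, and in which direction here, but not its likely size.

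**The case against.** - **One rule covers both arms, with one cap.** True, and the cap bounds the spread. If everyone ran to 30 minutes there would be no timing difference. But nothing requires that, and a shared rule does not equalise times between a device and no device.
- **Timing is partly recoverable.** VR duration is collected, and vitals are to be recorded electronically immediately after the intervention. For uninterrupted wear this gives approximate elapsed time. It does not cover pauses, Controls who end early, or the survey listed ahead of the pain score, and no analysis uses it. Timestamps would not undo stopping driven by response. Pain ratings from the health record, up to 96 hours after, could support a sensitivity analysis but are not the primary measure.
- **An end-of-session score is a legitimate target for distraction analgesia.** This is the strongest point. A fixed-time score in someone who stopped early answers a different question and may follow analgesia, which the protocol leaves unrestricted. That is a reason to keep the end-of-session score as secondary. It does not make the score comparable with a Control group that has no session to end.
- **The magnitudes rest on assumptions.** They do. At the gentlest slope with a 20-minute stop, type I error is only 5.2% to 5.5% across the SDs considered. The 40.7% figure combines the steepest slope, a universal 10-minute stop and the smallest SD.
- **The trial is sized on the within-group test.** The VR paired test is indeed unaffected by Control timing, although its own post score remains self-timed.

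**Conclusion.** The concern holds. As written, the plan permits the primary pain score to be taken at times that differ by arm and depend on response, and the between-arm analysis does not address it. Confidence is high that the definition is missing. The size and direction of the bias cannot be determined from the documents: scoring VR earlier while pain rises favours VR, whereas stopping VR because pain worsens counts against it. Under the drift assumptions above, the consequence ranges from negligible to a substantial fraction of the 13 mm target. This should be fixed, mainly because prevention is cheap and later correction may be impossible.

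**What to change.** 1. Define the primary pain score at one prespecified elapsed time in both arms, for example 30 minutes after start (headset on, or the matching start of observation in Control), whether or not VR is still in use. Take it before the repeat survey.
2. Amend Subject Participation End so that assessment continues to that time after a patient stops.
3. Record the actual assessment time, whether the headset is on, and any analgesia given before the score. Prespecify how scores after analgesia are analysed.
4. Keep the end-of-session score as a secondary VR measure. Pain ratings at the 10-minute blood pressure readings are optional, since they may interrupt the distraction.
5. Reconcile the session-length statements in Pre-Intervention Procedures, Subject Participation End and VR Software. Wear with breaks could fit both limits, but the text does not say so. State also how the symptom pause is counted.

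**Cost.** Protocol wording and three recorded items, with staff already at the bedside. Early stoppers would be asked to give one later rating, which changes when their participation ends. Their fixed-time score reflects less on-device effect and may follow analgesia; the secondary score and the analgesia record keep that visible.
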